4.0 PROTOCOL

4.1 Recruitment

Vaccinated and unvaccinated women and individuals will be invited to participate in a voluntary web-based surveillance. They will be followed prospectively as a cohort to collect data on attitudes and outcomes associated with vaccination. Recruitment will be targeted based on the inclusion criteria, regardless of vaccination status or intention. Recruitment will occur through a social media and traditional media campaign and through dissemination of recruitment materials by health care providers. The study will have a UBC supported website that will contain information as well as a link that for individuals to be directed to the study e-consent. Once the research data base is built, the link will route potentially interested participants to the study information and consent. For those individuals that expressed an interest in the study, the study team will send the website information once ethics approval has been obtained. We plan to engage with physicians, midwives, The Society of Obstetricians & Gynaecologists of Canada, Black Physicians of Canada, Indigenous Physicians Association of Canada, and La Leche League to reach a diverse study population. We plan to recruit from local maternity, family medicine, and midwifery clinics, like Pomegranate and the Vancouver Family Practice Centre, as well as on the REACH BC website. We will also engage with the Oak Tree Clinic and the Maternal Fetal Medicine Clinic at BC Women's Hospital. We plan to implement a poster campaign with QR codes as well as utilize social media posts to share the study website using Instagram, Facebook and Twitter. Study postcards will be distributed that contain the

inclusion criteria, study objectives and a QR code that will take a potential participant to the registry e-consent. As demographic data are collected from participants in the baseline survey, our team will be able to rapidly adjust the media campaign to target areas of the country or populations with lower enrollment.

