Data collected from individuals who do not receive COVID-19 vaccines will act as an internal comparison group. We will also capture self-identified gender through our online demographics questionnaire and examine differences by gender. The module on COVID-19 vaccination history will include type of vaccine received, number of doses and dosing interval. Vaccine safety endpoints will be coordinated with the Canadian National Vaccine Safety Network (CANVAS) endpoints: adverse events as detailed in data collection forms, severity and duration of adverse event, resultant medical visits (including to emergency department) or hospitalization, and treatments administered.

Pregnancy and infant safety outcomes measured are key outcomes identified by the Pan-Canadian, surveillance CANCOVID-Preg team. These major pregnancy complications/outcomes include but are not limited to gestational hypertension, gestational diabetes, placental abruption, infant birthweight, preterm birth, NICU admission, congenital anomalies, spontaneous abortion or termination, and stillbirth or neonatal death. Postnatally, including infants of women vaccinated during lactation, infant SARS-CoV-2 infection, hospitalization, growth parameters, and neurodevelopment (hyper vigilance) will be ascertained.

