4.5 Statistical Analysis and Metrics

To adequately power for comparisons of adverse events, we used estimates of vaccine-related adverse events (i.e. pain at injection site, redness, swelling, fever, fatigue, chills, headache, muscle pain, joint pain, grade 4 serious adverse events) from the subset of younger participants in the Pfizer vaccine trial, as an example (12). The rate of overall adverse events was 25%, and with a sample size of 451 in the vaccinated cohort we could estimate this prevalence with $\pm 4\%$ precision and 95% confidence. Sample sizes are highly feasible and will allow for comparison of adverse obstetrical and infant outcomes between vaccinated and unvaccinated participants. Given a sample size of 500 per group (vaccinated vs. unvaccinated) we would have 80% power to detect a minimum relative risk of 1.5.

The immunogenicity sub-study would require 89 participants, assuming 10% loss to follow up to estimate a 70% seroconversion rate with \pm 10% precision and 95% confidence. A seroconversion rate closer to 80% would require 68 participants. For comparisons of antibody levels, using estimates for the 18-55y age group (13) we would need approximately 48 participants to demonstrate a 10% difference in geometric mean titer with 95% power and assuming an attrition rate of 10% per visit.

The presence of any adverse outcomes (vaccine and pregnancy-related) will be compared between vaccinated and unvaccinated using time-varying Cox's proportional hazards models (14), stratified by vaccine type, and including important confounders. Effectiveness will be assessed descriptively through participant reporting of positive SARS-CoV-2 tests and COVID-19 diagnoses in vaccinated

and unvaccinated participants. Clinical features of breakthrough cases will be described in those vaccinated. Exploratory analyses will investigate differences between vaccinated and unvaccinated people. Clinical severity will be compared with unvaccinated people in the CANCOVID-Preg cohort. This will include tracking of infections with variants of concern where possible in both vaccinated and unvaccinated participants.

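### The stated 80% power for a relative risk of 1.5 with 500 per group names no baseline risk, outcome or alpha, and holds only for outcomes with an unvaccinated risk of roughly 13% or more

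*Protocol*

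**What the plan says.** Protocol section 4.5 first sizes the vaccinated cohort for the precision of a vaccine-reaction rate: "The rate of overall adverse events was 25%, and with a sample size of 451 in the vaccinated cohort". It then turns to the comparison of groups: "Sample sizes are highly feasible and will allow for comparison of adverse obstetrical and infant outcomes between vaccinated and unvaccinated participants". The power claim comes next: "Given a sample size of 500 per group (vaccinated vs. unvaccinated) we would have 80% power to detect a minimum relative risk of 1.5". No outcome, unvaccinated risk, alpha or sidedness is attached to that claim.

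Section 4.2 describes the outcomes in question: "These major pregnancy complications/outcomes include but are not limited to gestational hypertension, gestational diabetes, placental abruption". The list goes on through preterm birth, NICU admission and congenital anomalies to stillbirth or neonatal death. No frequency is given for any of them.

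Section 4.5 plans time-varying Cox models for the comparison, stratified by vaccine type and adjusted for confounders. Section 4.1 states that recruitment is "regardless of vaccination status or intention", so the sizes of the two groups are not controlled.

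**The concern.** For a fixed number per group, the power to detect a given relative risk rises with the comparator risk. A statement of 80% power for a relative risk of 1.5 therefore describes one baseline risk and the risks above it. Without that baseline, the sentence reads as if it applied to every obstetrical and infant outcome the registry collects, and the section 4.2 list mixes outcomes for which no single baseline is plausible.

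Safety is the first primary objective. Section 3.1 says the data are to guide vaccine advisory committees, and section 4.7 plans monthly public reports. If an outcome has a risk well below the implied baseline, a non-significant result could be taken as stronger evidence against a 50% increase than the sample can provide.

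**Working it through.** **Inputs from the protocol (section 4.5).** 500 vaccinated and 500 unvaccinated; power 80%; relative risk 1.5.

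**Inputs assumed, because the protocol does not state them for this claim.** Two-sided alpha 0.05; a comparison of two proportions with pooled variance under the null; no loss to follow-up; unvaccinated risk p0 varied.

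**Step 1: the plan's own figure.** The 80% cannot be reproduced from the stated inputs, because p0 and alpha are missing. It can only be solved backwards for p0. With p1 = 1.5 × p0 and p̄ = (p0 + p1)/2, the number per group is

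n = [1.960 × √(2p̄(1 − p̄)) + 0.842 × √(p1(1 − p1) + p0(1 − p0))]² / (p1 − p0)²

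At p0 = 0.131: p1 = 0.1965, p̄ = 0.16375 and p1 − p0 = 0.0655. The two terms in the numerator are 1.026 and 0.439, so n = (1.464/0.0655)² ≈ 500. The stated claim thus corresponds to an unvaccinated risk of about 13.1%.

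**Step 2: how far the threshold depends on the method.**

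| Method | Unvaccinated risk needed |
|---|---|
| Two proportions, two-sided 0.05 | 13.1% |
| Same, with continuity correction | 13.8% |
| Two proportions, one-sided 0.05 | 10.7% |
| Schoenfeld, 191 events for hazard ratio 1.5 | 15.3% |
| Freedman, 197 events for hazard ratio 1.5 | 15.8% |

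The event-based rows use two-sided 0.05. They convert events to risk by events = 500 × p0 + 500 × 1.5 × p0 = 1250 × p0, so 191/1250 = 15.3% and 197/1250 = 15.8%. If 1.5 is instead treated as a hazard ratio, with p1 = 1 − (1 − p0)^1.5, the 191 events are reached at p0 = 15.7%.

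**Step 3: lower baseline risks.** These risks are illustrative. Two-sided 0.05, 500:500:

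| Assumed unvaccinated risk | Power for RR 1.5 | Minimum RR at 80% power | n per group for RR 1.5 at 80% power |
|---|---|---|---|
| 13% | 80% | 1.50 | 505 |
| 10% | 67% | 1.59 | 686 |
| 5% | 37% | 1.92 | 1471 |
| 3% | 24% | 2.28 | 2518 |
| 1% | 11% | 3.67 | 7750 |

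Worked example at 5%: p1 − p0 = 0.025. The standard error is 0.01531 under the null and 0.01529 under the alternative. Power = Φ[(0.025 − 1.960 × 0.01531)/0.01529] = Φ(−0.33) ≈ 37%.

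**Step 4: unequal groups, 1000 in total, 13% unvaccinated risk.** With 800 vaccinated and 200 unvaccinated, power for a relative risk of 1.5 is about 57%. With the reverse split it is about 64%.

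**The case against.** The strongest defence is that nothing has been shown to be miscalculated. A baseline of about 13% reproduces the sentence, so the fault is an unstated assumption. That is right, and the point should not be put as an arithmetic error.

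A second defence is that section 4.5 goes on to speak of comparing the presence of any adverse outcomes, vaccine-related and pregnancy-related. This can be read as a composite, whose risk could exceed 13%. On that reading the claim may hold. But the power sentence is not limited to a composite, and it follows a statement about obstetrical and infant outcomes in general. If a composite was meant, saying so is the remedy.

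Third, the 13% depends on a test the protocol does not name and is not the planned Cox analysis. This also stands. The threshold should be quoted as a range, but no variant tried brings it below about 11%.

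Three stronger readings are tempting and not supported:

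- A reader might infer that the 25% event rate in the same paragraph is the intended comparator and so contradicts the relative risk of 1.5. It is not offered as one. It is a vaccine-reaction rate, used only for the precision of an estimate in the vaccinated cohort.
- A reader might infer that the study is underpowered for particular named outcomes by a known amount. The protocol gives no outcome frequencies, so the lower-risk figures are conditional on assumed risks.
- A reader might infer that a 500:500 enrolment is forecast and will fail. The wording is conditional on that size. Uncontrolled recruitment makes imbalance possible but does not establish it.

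Nor does the protocol say that a non-significant result will be read as reassurance. That risk is an inference from the intended use of the data. How rare outcomes are to be presented can be left to the SAP.

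**Conclusion.** The point holds as a defect in a stated claim. The protocol gives a single power figure for a class of outcomes to which a single figure cannot apply. With 500 per group, 80% power for a relative risk of 1.5 requires an unvaccinated risk, for a single outcome or a composite, of about 13% on a two-sided 0.05 two-proportion test. Across the methods tried, the threshold runs from about 11% to about 16%. The claim does not hold for any listed outcome below that range, and the shortfall grows quickly as the risk falls: at an assumed 5%, power is less than half the stated figure.

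This rests on equal groups, no loss to follow-up, and no allowance for confounder adjustment or stratification by vaccine type, which would generally lower power further. Which listed outcomes fall below the threshold cannot be settled from the protocol.

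**What to change.** Rewrite the power sentence in section 4.5 so that it:

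- names the outcome or composite to which the 80% applies, with the assumed unvaccinated risk and its source, the alpha and the sidedness;
- limits the claim of 80% power for a relative risk of 1.5 to outcomes at or above that risk;
- gives the minimum detectable relative risk over a range of lower risks, computed by the method the sponsor adopts (the table above can serve if that is a two-sided 0.05 two-proportion test).

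Optionally, add a line that an unequal split lowers power, stating which group is the larger.

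The cost is protocol wording only, with no change to design or data collection. The drawback is that the stated power becomes less favourable.

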Data collection and time points Data collection and timepoints for immune sub-study	 Baseline survey administered at start of enrollment 2 time-based follow up surveys administered: December 1st 2023 and February 1st 2024 Reminders to follow up surveys will be sent out periodically throughout study duration Access to previously collected antenatal samples Maternal/gestational parent blood samples will be collected four weeks to up to one day before vaccination, four weeks after vaccination, 12 weeks after vaccination, delivery +/- 2 days, and 4-6 weeks after delivery
	 weeks after delivery. Umbilical Cord blood samples at delivery and infant blood samples and breast milk at 4-6 weeks post delivery

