4.6 Statistical Analysis for the Immune Sub-Study

Seroconversion will be estimated and compared to licensure data using binomial tests. Antibody levels in pregnancy will be compared to licensure data for the relevant vaccine and dose using one-sample t-tests. We will stratify by gestational age, participant age, and other co-factors that might influence immune response. Maternal antibody levels will be compared to infant levels at birth, controlling for infant gestational age at delivery, birth weight, and infant feeding. Exploratory analysis of antibodies in breast milk will be compared to maternal serum antibody levels.

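### Taken literally, 48 participants give 95% power for a 10% difference in geometric mean titre only if the between-person geometric SD is about 1.2 or less, and the protocol states no SD

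*Protocol*

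**What the plan says.** Section 4.5 sizes the immune sub-study twice in one paragraph.

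- Seroconversion: "The immunogenicity sub-study would require 89 participants, assuming 10% loss to follow up", to estimate a 70% rate to within 10 percentage points. If the rate is nearer 80%, 68 participants are said to suffice.
- Antibody levels: "we would need approximately 48 participants to demonstrate a 10% difference in geometric mean titer with 95% power", "assuming an attrition rate of 10% per visit". The basis is described only as estimates for adults aged 18-55 from a cited publication. No SD, alpha, sidedness or number of visits is given.

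Section 4.6 names the test: "Antibody levels in pregnancy will be compared to licensure data for the relevant vaccine and dose using one-sample t-tests". The Summary lists five maternal blood draws: before vaccination, 4 and 12 weeks after it, at delivery, and 4-6 weeks after delivery. Immunogenicity is one of the five primary objectives in section 2.0.

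**The concern.** Titres are normally compared on a log scale, where a 10% difference is small: ln(1.10) = 0.0953, or 0.041 in log10 units. Detecting a shift of that size with 95% power and a few dozen people requires titres that barely differ between people. The protocol shows no SD that would support this.

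What is at stake is how a null result is read. The protocol fixes the effect, the power and the number together. A non-significant comparison with licensure data could therefore be taken as evidence against a difference as small as 10%, when the sub-study might miss much larger ones. Section 4.7 plans monthly public reports, so such a reading could travel.

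**Working it through.** **Inputs.** From section 4.5: n = 48, effect 10% in geometric mean titre (GMT), power 95%, attrition 10% per visit, 89 planned for seroconversion at 70% (68 at 80%). From section 4.6: one-sample t-test. From the Summary: five maternal draws, hence four after the first. Assumed: two-sided alpha 0.05, analysis on log titre. Not given: the SD.

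**The plan's own figures.** The two seroconversion sizes reproduce: 1.96² × 0.7 × 0.3 / 0.1² = 80.7, and × 1.1 = 88.7, so 89; 1.96² × 0.8 × 0.2 / 0.1² = 61.5, and × 1.1 = 67.6, so 68. The 48 cannot be reproduced forward without an SD, so it is inverted.

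**Step 1: the SD that the 48 implies.** Let d be the standardised difference that gives 95% power under the noncentral t. Then the SD of ln titre = ln(1.10)/d, and the geometric SD (GSD) = exp(SD).

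| Analysed | d | SD of ln titre | Largest GSD |
|---|---|---|---|
| 48 | 0.531 | 0.179 | 1.196 |
| 31 (48 × 0.9⁴ = 31.5) | 0.669 | 0.142 | 1.153 |
| 89 | 0.386 | 0.247 | 1.28 |
| 58 (89 × 0.9⁴ = 58.4) | 0.482 | 0.198 | 1.22 |

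Starting from 48, the one-sample variants (ratio 0.90 instead of 1.10, one-sided alpha 0.05, none to five rounds of attrition) all fall between 1.14 and 1.24. A two-sample test with 24 per group would need about 1.09-1.10.

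**Step 2: what a GSD of 1.15-1.20 means.** About 95% of people would lie within GSD^1.96 of the geometric mean: 1.196^1.96 = 1.42-fold, or 1.153^1.96 = 1.32-fold.

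**Step 3: against the protocol's own seroconversion rate.** Suppose a proportion p seroconverts, the two groups' geometric means differ by a factor R, and there is no other variation. Then SD = ln(R) × √(p(1−p)).

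- R = 2, p = 0.7: 0.693 × 0.458 = 0.318, GSD 1.37.
- R = 2, p = 0.8: 0.693 × 0.400 = 0.277, GSD 1.32.
- Largest R compatible with SD 0.179: exp(0.179/0.458) = 1.48 at 70% and exp(0.179/0.400) = 1.57 at 80%.

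This applies only if non-seroconverters' titres are analysed. Section 4.6 does not exclude them.

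**Step 4: power for a ratio of 1.10 over an assumed range of GSD.**

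| GSD (assumed) | n = 48 | n = 89 | Completers for 95% power |
|---|---|---|---|
| 1.3 | 69% | 92% | about 99 |
| 1.5 | 36% | 59% | about 236 |
| 2 | 15% | 25% | about 688 |
| 3 | 9% | 12% | about 1,727 |

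The last column is the normal approximation, [(1.96 + 1.645) × ln(GSD)/ln(1.10)]², rounded up.

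**Step 5: the GMT ratio detectable with 95% power if GSD = 2.** Ratio = 2^d by exact t: 1.45 at n = 48, 1.59 at n = 31, 1.31 at n = 89, 1.40 at n = 58.

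**Step 6: an alternative origin for the 48.** If the 10% was applied to the mean log10 titre, the tolerated log10 SD is 0.1 × L × √n/3.605, where L is the log10 GMT. For L from 2 to 5 (assumed) and n from 28 to 48, this allows a GSD of about 2 to 9.

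**The case against.** The strongest reply is that everything turns on an SD that cannot be seen. The protocol does point to a source, and if titres there were tight enough the 48 would be right. That stands: the larger GSDs in the table are assumptions, and close to the threshold the shortfall is moderate (83% power at GSD 1.25 with n = 48).

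Second, the sub-study plans 89 participants, or 68 if seroconversion is higher; 48 is only the smaller requirement for one comparison. That also stands, and is why results for 89 are shown. It softens the point without removing it: even with all 89 analysed the tolerable GSD is 1.28, and power at GSD 2 is 25%.

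Third, 48 may be correct for another effect, such as 10% of the mean log titre. That is possible but unproven. If so, the effect is misdescribed: 10% of a log10 mean of 3, for instance, is 0.3 log10 units, a 2-fold difference in titre.

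A reader might also infer that the two attrition assumptions, 10% overall for the 89 and 10% per visit for the 48, contradict each other. The document does not support that. If seroconversion is read at one post-vaccination visit, 89 × 0.9 = 80, and 1.96 × √(0.21/80) gives ±10.0 points, as stated. A per-visit rate is natural for comparisons across serial visits.

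Finally, the protocol claims neither equivalence nor non-inferiority, so the misreading of a null result is a risk, not something the plan commits to.

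**Conclusion.** The point holds conditionally. As literally written, the combination of 48 participants, a 10% difference in GMT and 95% power requires a GSD of no more than about 1.15-1.20. This rests on the one-sample t-test of section 4.6 and an assumed two-sided alpha of 0.05. No SD is given, and so small a spread sits poorly with 70-80% seroconversion if non-seroconverters are included.

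A reader might infer that the sub-study is shown to lack the stated power. The document does not support that, because the SD lies in a source that is not at hand. What can be said is that the figure cannot be reproduced, and that it fails at any spread above about 1.2 with 48 analysed, or about 1.28 with 89. How far it fails depends on the spread: power at n = 48 runs from 69% at GSD 1.3 to 9% at GSD 3.

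This is more than a detail left to a statistical analysis plan, because the protocol itself states the number, the effect and the power. The sentence should be corrected; the design need not change.

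**What to change.** In section 4.5:

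1. State the SD of log titre taken from the cited source, the scale on which the 10% is defined, alpha and sidedness, and which visits enter the attrition calculation.
2. Replace the claim of "a 10% difference in geometric mean titer" with 95% power by the GMT ratio detectable with the expected evaluable number. If the GSD is 2, that ratio is about 1.31-1.40 with 58-89 evaluable, or 1.45-1.59 with 31-48. Use the actual SD once it is stated.
3. If the 48 was derived for a difference in mean log titre, describe that effect and give the titre ratio it corresponds to.

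The cost is protocol wording and one recalculation. No extra participants are needed, but the stated sensitivity may look less favourable.

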4.2 Data Collection

Once consent has been obtained, the baseline survey will automatically be pushed to the participant. The baseline answers will determine if pregnancy and or vaccine outcome surveys are to be answered at the same time. A short follow-up questionnaire will be administered on December 1st 2023 and another on February 1st 2024 to capture changes in vaccination status, COVID-19 status, pregnancy outcomes or significant health events. The follow-up surveys will determine if/when outcome surveys need to be completed. If consent is withdrawn, the study will immediately cease for the participant. The survey modules are as follows:

1. Baseline survey: Pregnancy status, vaccination status, demographics, health history, COVID-19 history & pregnancy history - Administered at enrollment starting Sept 1, 2023 until Jan 31, 2024

2. Pregnancy Outcomes: Pregnancy & infant outcomes – Administered if pregnancy started in 2023 and are not currently pregnant

3. Vaccine Outcomes: Answered if a dose of a COVID-19 vaccine received during the current pregnancy

4. Vaccine Attitudes 1: Feelings, opinions & attitudes towards vaccines– Administered at end of surveys received at baseline

5. Vaccine Attitudes 2: Feelings, opinions, and attitudes towards the Respiratory syncytial virus (RSV) – Administered following the completion of Vaccine Attitudes 1

6. Follow-up survey: 2 time-based follow-up surveys administered on December 1st, 2023, and on February 1st, 2024 with reminders sent out periodically throughout study duration
7. Health Event: Significant health events resulting in a visit to the emergency department or hospitalization – Administered if triggered by Follow-up survey

In the event of an adverse reaction or major health event, the study team will contact a participant for further health information.

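### Section 4.5 compares vaccine-related adverse events between vaccinated and unvaccinated participants, but the module that collects them goes only to people dosed in the current pregnancy

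*Protocol*

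**What the plan says.** Section 4.5 sets out the comparative safety analysis: "The presence of any adverse outcomes (vaccine and pregnancy-related) will be compared between vaccinated and unvaccinated". The method is a time-varying Cox model, and these models are "stratified by vaccine type, and including important confounders". The same section lists the events it counts as vaccine-related. They are local reactions at the injection site, general symptoms such as fever, tiredness and headache, and grade 4 serious events. It takes their overall rate as 25% and derives 451 vaccinated participants for a precision of ±4 percentage points. It then claims 80% power for a relative risk of 1.5 with 500 per group, in connection with obstetric and infant outcomes.

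Section 4.2 fixes who is asked what:

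- "Vaccine Outcomes: Answered if a dose of a COVID-19 vaccine received during the current pregnancy".
- Pregnancy Outcomes depends on the pregnancy having started in 2023 and ended, not on vaccination.
- The two follow-up surveys are meant "to capture changes in vaccination status, COVID-19 status, pregnancy outcomes or significant health events", with no vaccination condition.
- "Health Event: Significant health events resulting in a visit to the emergency department or hospitalization" is a separate module, "Administered if triggered by Follow-up survey".

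Section 4.2 also makes participants who receive no COVID-19 vaccine the internal comparison group.

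**The concern.** The analysis text promises a two-group comparison of events for which the survey, as described, has only one group's answers. A local reaction cannot occur without an injection. Fever or headache can occur in anyone, but no listed module is described as asking the unvaccinated about them. A zero in the comparator would then mean that the question was not asked, not that the symptom was absent.

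Safety is primary objective 1, and this is the comparative model named for it. Section 4.7 commits to monthly reports that are also shared publicly, and section 1.2 notes that this population has historically had lower vaccine confidence. An apparent excess of adverse outcomes produced by survey routing could reach that audience directly. An SAP can redefine the endpoint, but it cannot recover symptoms that were never asked of the comparison group.

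**Working it through.** **1. The plan's own figure.** Inputs from section 4.5: p = 0.25, d = 0.04, 95% confidence.

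n = z²p(1−p)/d² = 1.96² × 0.25 × 0.75 / 0.04² = 450.2, rounded up to 451.

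The figure reproduces. It is a one-group precision calculation for the vaccinated, although the paragraph introduces it as powering comparisons of adverse events.

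**2. Vaccine-related events alone.** With 500 simulated participants per group, 125 events in the vaccinated (25%) and none possible in the unvaccinated, the Cox partial log-likelihood is:

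| log HR | log-likelihood |
|---|---|
| 0 | −855.376 |
| 2 | −777.915 |
| 5 | −760.815 |
| 10 | −759.857 |
| 20 | −759.851 |

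It never turns down, so no finite hazard ratio exists.

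**3. A composite of both kinds of event.** Let r be the background risk of a pregnancy-related adverse outcome, the same in both groups (no true effect). Let 25% of the vaccinated also report a vaccine event, independently of r. The protocol gives no r, so the values below are assumptions.

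- Recorded risk in the vaccinated: r + 0.25(1−r). Recorded risk in the unvaccinated: r.
- Apparent RR = [r + 0.25(1−r)]/r = 0.75 + 0.25/r.
- Apparent HR, with constant hazards over a common period = 1 + ln(0.75)/ln(1−r).

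| Assumed r | Risk, vaccinated | RR | HR |
|---|---|---|---|
| 30% | 47.5% | 1.58 | 1.81 |
| 25% | 43.75% | 1.75 | 2.00 |
| 13% | 34.75% | 2.67 | 3.07 |
| 8% | 31.0% | 3.88 | 4.45 |
| 5% | 28.75% | 5.75 | 6.61 |

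Setting 0.75 + 0.25/r = 1.5 gives r = 1/3. The spurious RR therefore exceeds the target of 1.5 whenever the background risk is below about 33%. The 13% row is informative because 500 per group gives 80% power for RR 1.5 at a background risk of about 13.1% (two-sided 5% assumed).

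**4. Vaccine type.** Two codings were tried on simulated null data, 500 per group with three vaccine types:

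- Type as literal Cox strata, with the unvaccinated as a stratum of their own. Vaccination does not vary within any stratum, and the log-likelihood is −882.354 at log HR −2, 0 and 2. The effect cannot be estimated.
- Separate models of each type against all unvaccinated. The estimates are ordinary: log HR −0.40, −0.30 and 0.16, with standard errors 0.26, 0.24 and 0.21.

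**The case against.** A reader might infer that the whole safety comparison is meaningless. The protocol does not support that. Pregnancy Outcomes, the follow-up surveys and Health Event do not depend on vaccination, so pregnancy and infant outcomes, and emergency visits or hospitalisations reported at follow-up, come from both groups. Serious events on the section 4.5 list may also surface by that route. The two-group power claim is tied to obstetric and infant outcomes and the 451 to the vaccinated, which suggests the authors had the right split in mind. The sentence describing the analysis does not make that split.

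A reader might also infer that stratifying by vaccine type makes the model impossible to fit. That follows only from one literal coding. Section 4.6 uses the same verb alongside binomial and one-sample t-tests, where it most naturally means subgroup analyses. In that sense type-versus-unvaccinated models are estimable. Because the exposure is time-varying, pre-dose person-time could also sit in the stratum of the type eventually received. This is an ambiguity, not a demonstrated failure.

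A third inference is that events before enrolment are missed only in the unvaccinated, because Health Event is triggered at follow-up. That is not established. The baseline survey asks everyone about health history, and the data collection forms are not shown. The same gap means that general symptoms might be asked of everyone somewhere, although the module list gives no sign of it.

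Finally, section 4.5 defines no composite and speaks of models in the plural. The ratios in step 3 apply only if the two kinds of event are pooled, a reading that its reference to any adverse outcome permits. If they are kept apart, step 2 applies to the vaccine-related part.

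**Conclusion.** The concern holds for vaccine-related events and for any composite that contains them. As written, section 4.5 asks for a contrast that the routing in section 4.2 cannot supply. On their own these events give no finite hazard ratio. Pooled with pregnancy outcomes they push the risk ratio upward: 1.75, 2.7 and 3.9 at background risks of 25%, 13% and 8%.

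These sizes rest on the following assumptions:

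- the protocol's 25% rate applies to the whole vaccinated group, meaning that all were dosed in the current pregnancy (a group that includes people vaccinated only before pregnancy would dilute the effect);
- vaccine and pregnancy events are independent;
- there is no true effect on pregnancy outcomes;
- the background risks are as assumed;
- the unseen forms do not ask the unvaccinated the same symptom questions.

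The direction of the bias does not depend on the background risk. The comparison of pregnancy and infant outcomes and of follow-up health events stands. The wording on vaccine type needs clarifying only.

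**What to change.** In section 4.5, or in the SAP if it governs:

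- Report solicited vaccine reactions in the vaccinated only, as proportions with 95% confidence intervals by vaccine type. This is what the 451 figure supports.
- Restrict the vaccinated-versus-unvaccinated Cox comparison to outcomes asked identically of both groups over the same window, and exclude vaccine-reaction events from any composite.
- Replace the phrase on stratification with vaccine type as levels of the time-varying exposure, with unvaccinated person-time as the shared reference, or with separate type-versus-unvaccinated contrasts.

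This is a change of wording. The cost is that reactogenicity symptoms have no between-group estimate. If one is wanted, both groups would have to be asked the same symptom questions over matched windows, which adds to the survey.
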